9.3 POPULATIONS FOR ANALYSES

The following populations are defined (Table 20).

Table 20 - Populations for analyses

Population	Description
Enrolled	All participants who sign the ICF and have been allocated to an intervention regardless of whether the intervention was received or not.
DLT-evaluable (only for Part-1 and Part-3A)	Participants who take at least 4 of the 6 planned doses of SAR442720 and 28 of the 42 planned doses of adagrasib in the first cycle of the treatment and complete the DLT observation period. OR Participants who have any DLT observed in the DLT or DLT observation period.
PK	Participants who have at least one measurable SAR442720 concentration or at least one measurable pembrolizumab concentration or at least one measurable adagrasib concentration after the first dose
PDy	Participants who have at least one PDy marker result after the first dose
Safety	Participants who take at least one dose of any drug (ie, SAR442720, pembrolizumab or adagrasib)

Abbreviations: DLT = dose-limiting toxicity, ICF = informed consent form, PDy = pharmacodynamics(s), PK = pharmacokinetic(s).

9.4 STATISTICAL ANALYSES

The statistical analysis plan will be finalized prior to database lock and it will include a more technical and detailed description of the statistical analyses described in this section. This section is a summary of the planned statistical analyses of the most important endpoints including primary and key secondary endpoints.

9.4.1 General considerations

All baselines are defined as the last assessment prior to the first dose unless specified otherwise. The MTD recommendation will be based on the DLT-evaluable population Cycle 1 data only. All safety and efficacy analyses will be based on the safety population unless otherwise specified. The Part-1 and Part-3A analyses will be performed separately by different dose levels unless specified otherwise. The Part-2 and Part-3B analyses will be presented separately, with Part-2 presented by different cohorts and overall, and Part-3B as a single cohort.

The analysis period will be divided into 3 segments:

- The pre-treatment period is defined as the time from when the participants give informed consent to the first administration of the IMP.
- The treatment period (ie, treatment-emergent period) is defined as the time from the first administration of IMP up to 30 days after the last administration of IMP.
- The post-treatment period is defined as the time from the 31 days after the last administration of IMP.

9.4.2 Efficacy endpoint(s)

Below table (Table 21) summarizes the efficacy endpoints involved in this study:

Table 21 - Summary of efficacy endpoints

Efficacy Endpoint	Part-1/3A	Part-2/3B	Part-4
ORR per RECIST v1.1	Secondary	Primary	Secondary
DoR	Secondary	Secondary	Secondary
PFS	NA	Secondary	NA
TTR	NA	Secondary	NA
CBR	NA	Secondary	NA
DCR	NA	Secondary	NA
OS	NA	Exploratory (only for Part-2)	NA
ORR per iRECIST	NA	Exploratory (only for Part-2)	NA

Abbreviations: CBR = Clinical benefit rate; DCR = disease control rate; DoR = duration of response, NA = not applicable; ORR = objective response rate, OS = overall survival; PFS = progression free survival, RECIST= Response Evaluation Criteria in Solid Tumors; TTR = time to response.

The ORR is defined as the proportion of participants who achieve a confirmed complete response (CR) or partial response (PR) per RECIST v1.1. Objective response rate and the corresponding 90% Clopper-Pearson 2-sided CI will be derived. Best overall response (BoR) per RECIST v1.1 will also be summarized. ORR per iRECIST will also be presented (for Part-2 only).

For Part-2 and Part-3B, the primary endpoint (ORR) analyses is performed when all participants have at least 2 post baseline tumor assessments with response durability demonstrated or discontinue study treatment (whichever occurs first).

Duration of response per RECIST v1.1 is defined as the interval from the first documentation of CR or PR to the earlier of the first documentation of definitive disease progression or death due to any cause, whichever occurs first. Progression free survival per RECIST v1.1 is defined as the interval from the administration of the first IMP dose to the earlier of the first documentation of definitive disease progression or death due to any cause, whichever occurs first. Participants who are still alive and free from progression at the time of data cutoff date, are lost to follow-up, have discontinued from the study, or who have initiated subsequent anticancer therapy will be censored at the last adequate tumor assessment. The Kaplan-Meier estimates of the 25th, 50th, and 75th percentiles and their associated 95% CI will be provided. The OS will also be summarized using Kaplan-Meier methods.

Time to response is defined as the interval from the administration of the first IMP dose to the first documented CR or PR which is confirmed by a subsequent response. The TTR will be summarized descriptively.

Clinical benefit rate is defined as the proportion of participants who achieved confirmed CR or PR at any time or SD for at least 6 months. The CBR and corresponding 90% Clopper Pearson 2-sided CI will be derived.

Disease control rate is defined as the proportion of participants who achieved confirmed CR or PR or SD. The DCR and corresponding 90% Clopper-Pearson 2-sided CI will be derived.

9.4.3 Safety endpoint(s)

Safety endpoints including incidence and severity of AEs and SAEs and laboratory abnormalities are the primary endpoints for Part-1 and Part-3A and secondary endpoint for Part-2, Part-3B, and Part-4.

9.4.3.1 Adverse events

The TEAE period is defined as the time from the first dose of study interventions up to 30 days after last dose of study interventions. Only TEAEs will be summarized in tables.

An overall summary of TEAEs will be provided. The number and percentage of participants who experience any of the following will be provided:

- TEAEs
- TEAEs of Grade ≥ 3
- Grade 5 TEAE (any TEAE with a fatal outcome during the treatment period)
- Serious TEAEs
- Serious treatment-related TEAEs
- TEAE leading to premature discontinuation of either SAR442720, pembrolizumab or adagrasib
- TEAE leading to definitive discontinuation
- TEAE leading to dose modifications
- Treatment-related TEAEs.
- Treatment-related TEAEs of Grade ≥ 3
- DLTs

The number and percentage of participants experiencing TEAEs by primary system organ class and PT will be summarized by NCI CTCAE version 5.0 grade (all grades and Grade ≥ 3). Similar tables will be prepared for treatment-related TEAEs, AESIs, TEAEs leading to treatment discontinuation, TEAEs leading to dose modification, delay, omission, serious TEAEs and TEAEs with fatal outcome.

9.4.3.2 Clinical laboratory evaluations

Clinical laboratory test results will be graded according to NCI CTCAE Version 5.0, when applicable. Number (%) of participants with laboratory abnormalities (ie, all grades and Grade ≥ 3) using the worst grade during the TEAE period will be provided for the all-treated population.

When the NCI CTCAE Version 5.0 scale is not applicable, the number of participants with laboratory abnormality out-of-normal laboratory range value and potential clinically significant assessments will be displayed.

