E 22. Medication and supplements that may interfere or potentiate with SAR442720 and/or adagrasib metabolism or toxicity PRIOR or DURING study intervention are excluded:

- Strong CYP3A4 inducers or inhibitors (within 7 days prior)
- Strong P-glycoprotein (P-gp) inhibitors (eg, cyclosporine, tacrolimus; within 7 days prior)
- Strong Breast Cancer Resistance Protein (BCRP) inhibitors (eg, eltrombopag; within 7 days prior) (applies to Part-3 only)
- Proton pump inhibitors (within 3 days prior) or H2-receptor antagonists (within 1 day prior) during the dose escalation portion of the study
- Medications known to prolong QTc interval
- Acetylsalicylic acid (low dose aspirin, anticoagulation with low-molecular weight heparin or direct Factor X inhibitors and LMWH are allowed. Prophylactic LMWH is also allowed for high risk patients with hypercoagulability).

Diagnostic assessments

E 23. Inadequate organ and bone marrow function at the Screening visit:

- Absolute neutrophil count (ANC) $<1000 \mu\text{L} (1 \times 10^9/\text{L})$.
- Platelets $<100 \times 10^3 \mu\text{L}$ (after at least 3 days without platelet transfusion).
- Hemoglobin $<9 \text{ g/dL}$ or $<5.6 \text{ mmol/L}$ (without transfusions within 2 weeks of initiation of IMP).
- Total bilirubin $>2 \times \text{ULN}$.
- AST and/or ALT $>3 \times \text{ULN}$ (or $>5 \times \text{ULN}$ for participants with liver metastases).
- Blood creatinine $>1.5 \times \text{ULN}$ or creatinine clearance of $<50 \text{ mL/min}$ (using Cockcroft Gault formula or 24-hour urine collection)
- Prothrombin time (PT)/international normalized ratio (INR) and activated partial thromboplastin time or partial thromboplastin time (aPTT/PTT) $>1.3 \times \text{ULN}$ or outside the therapeutic range of the local laboratory if receiving therapeutic anticoagulation that would affect the PT/INR.

Other exclusions

E 24. Individuals accommodated in an institution because of regulatory or legal order; prisoners or participants who are legally institutionalized.

E 25. Participant not suitable for participation, whatever the reason, as judged by the Investigator, including medical or clinical conditions, or participants potentially at risk of noncompliance to study procedures.

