Section 2.3.1 Risk assessment	The following statement was removed: “Phototoxicity studies with SAR442720 have not been completed. Therefore, participants taking SAR442720 should use appropriate protection when exposed to UV radiation”	In vitro and in vivo studies have been conducted and no indication of phototoxicity was observed. This information is included in the SAR442720 Investigator’s Brochure (IB) v3.
	The following text, “approximately 6.4x of unbound C _{max} ”, was adjusted to “approximately 17x of unbound C _{max} ”.	Clarification.
	The following paragraph was added: “Emerging data from ongoing studies identifies anemia as a new potential risk based on clinical data and preclinical evidence. In the monotherapy study (n=82), anemia AEs (Standardized MedDRA Query [SMQ]), of any grade, were reported in 26 (31.7%) participants, including 11 (13.4%) participants who required blood transfusions. Grade 3 anemia events were reported in 13 (15.9%) participants; 3 SAE including 1 event related to study drug. No Grade 4 anemia events have been reported to date. Median time to onset of anemia was 22 days from the start of study treatment, and median time to recovery was 21 days. In addition, 54 (65.9%) participants had a hemoglobin grade shift from baseline, of which 27 participants were anemic at baseline, among which 3 (3.7%) participants had a hemoglobin shift from Grade 1 to Grade 3 and 5 (6.1%) participants had a hemoglobin shift from Grade 2 to Grade 3. The other 27 participants were normal at baseline, among which 6 (7.3%) participants had a Grade 2 worsening and 2 (2.4%) participants had a Grade 3 worsening.”	Anemia is the third risk which has been identified as potential risk. It was added to the protocol as to alert the investigators.

Section # and Name	Description of Change	Brief Rationale

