#### **4.7.2 Laboratory variables**

Hematological and clinical biochemistry toxicities will be assessed from laboratory test parameters.

A summary table will present the frequency of patients with any grade of abnormal laboratory tests and with Grade $\geq$  3 abnormal laboratory tests occurring during on-treatment period. For patients with multiple occurrences of the same laboratory variable during the treatment, the maximum grade (worst) per patient will be used. The denominator used for percentage calculation is the number of patients with at least 1 evaluation of the laboratory test during the considered observation period. For laboratory tests for which NCI-CTCAE V5.0 scale is not applicable, the frequency of evaluable patients outside normal ranges will be provided.

If relevant, selected laboratory tests will be plotted describing mean changes from baseline and associated +/- STD throughout the on-treatment period.

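### The laboratory table counts each participant's worst on-treatment grade without reference to baseline, so its all-grades column includes abnormalities already present at entry

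*Protocol*

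**What the plan says.** Protocol 9.4.3.2 grades laboratory results by CTCAE version 5.0. The number and percentage of participants with an abnormality, for all grades and for Grade 3 or higher, "using the worst grade during the TEAE period will be provided for the all-treated population".

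SAP 4.7.2 introduces its results as hematological and biochemical toxicities. It then plans the same output: "A summary table will present the frequency of patients with any grade of abnormal laboratory tests", with a second count for Grade 3 or higher. Where a test is abnormal more than once, "the maximum grade (worst) per patient will be used". The SAP adds a denominator rule: "The denominator used for percentage calculation is the number of patients with at least 1 evaluation of the laboratory test during the considered observation period". The only output in that section that refers to baseline is a conditional plot of mean changes for selected tests.

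Protocol 9.4.3 gives these results endpoint status: "Safety endpoints including incidence and severity of AEs and SAEs and laboratory abnormalities are the primary endpoints for Part-1 and Part-3A", and secondary in the other parts. SAP 4.3 repeats this. The statistical considerations in the protocol synopsis instead list laboratory results as secondary for Part-1 and Part-3A.

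Entry limits are in exclusion criterion E23, under "Inadequate organ and bone marrow function at the Screening visit". SAP 5.4, on unscheduled visits, mentions shift summaries for safety in passing.

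**The concern.** A worst on-treatment grade describes the participant's state, not a change in it. Someone who enters with Grade 1 anemia and stays at Grade 1 is counted in the all-grades column exactly like someone who became anemic on treatment. In a randomized trial a control arm would show how much of the count is background. This trial has none, so each participant's own baseline is the only reference for a drug effect, and this table does not use it.

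Anemia is one of the potential risks of SAR442720 listed in protocol Table 11, and escalation dose levels hold 3 to 6 participants. One or two persisting entry abnormalities can change the apparent any-grade rate at a dose level considerably. What is at stake is how a named safety endpoint is read.

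**Working it through.** **1. Rules compared**

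| Data | Source | Reference to change or baseline |
|---|---|---|
| Adverse events | SAP 4.3 | Must develop, worsen or become serious on treatment |
| ECG | SAP 4.7.3 | Reported overall and by baseline status (normal/missing, abnormal) |
| Vital signs | SAP 5.6 | Every criterion includes a change from baseline |
| Laboratory grades | Protocol 9.4.3.2, SAP 4.7.2 | None |

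Baseline itself is defined in protocol 9.4.1 and SAP 4.1, so the missing piece is only its use.

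**2. Can participants enter with abnormal values?** Yes. E23 excludes hemoglobin only below 9 g/dL, neutrophils only below 1 x 10^9/L, AST/ALT only above 3 x ULN (5 x with liver metastases) and bilirubin only above 2 x ULN. Protocol Table 27 itself provides for a baseline Grade 2 AST or ALT elevation. In the monotherapy data quoted in the protocol amendment history (used here only as data, n = 82), some participants had Grade 1 or Grade 2 hemoglobin at baseline.

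**3. What do those monotherapy data say about size?** They report that "54 (65.9%) participants had a hemoglobin grade shift from baseline, of which 27 participants were anemic at baseline".

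- Check of the stated figure: 54/82 = 65.9%. It reproduces.
- Anemic at baseline and shifted: 27/82 = 32.9%.
- Not shifted: 82 - 54 = 28. Let u be the number of these who were anemic at entry; u is not given and lies between 0 and 28.

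Assume that the shifts were worsenings and that entry anemia was seen again on treatment. Then:

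- New-or-worsened count: 54/82 = 65.9%.
- Worst-grade count: (54 + u)/82, which is 65.9% at u = 0, 82.9% at u = 14 and 100% at u = 28.
- Excess: u/82, from 0 to 34.1 percentage points.

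The quantity of interest is u, and the documents do not state it.

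**4. Illustration for this trial.** Let p be the share entering with an any-grade hemoglobin abnormality that persists without worsening. The expected count with no drug effect is n x p. For an assumed p of 10% to 40%:

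- n = 40 (Part-2 overall, or Part-3B): 4 to 16
- n = 20 (one Part-2 cohort): 2 to 8
- n = 6 (one dose level): 0.6 to 2.4

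**5. Grade 3 or higher column.** E23 requires platelets of at least 100 x 10^3/µL, while protocol Table 11 places Grade 3-4 below 50 000. For liver metastases, Table 27 speaks of a baseline elevation of Grade 2. For tests limited in this way, a Grade 3 value on treatment will normally be a worsening. Lipase and lymphocytes are in protocol Table 22 but have no limit in E23, so that protection does not extend to them.

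**The case against.** Several arguments on the other side stand at least in part.

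- **Endpoint status.** A reader of protocol 9.4.3 might infer that a primary endpoint is affected in Part-1 and Part-3A. The documents conflict: the synopsis lists laboratory results as secondary there, and the objectives tables name DLTs, TEAEs and SAEs as the primary endpoints. Only the status of a named safety endpoint can be claimed.
- **Dose decisions.** A reader might infer that the MTD recommendation is distorted. It is not: under protocol 9.4.1 it rests on Cycle 1 data in the DLT-evaluable population. No decision rule uses this table, and no formal test is planned.
- **Size.** It is tempting to apply 27/82 to this trial and conclude that about 13 of 40 (0.329 x 40 = 13.2) would be counted falsely. The documents do not support this. Those 27 also shifted grade, so if they worsened, a new-or-worsened rule would count them too. The data also come from another population, whereas Part-2 enrols participants without prior systemic therapy for advanced disease.
- **Reporting elsewhere.** Clinically significant laboratory changes can be recorded as adverse events (protocol Appendix 3), and Grade 3 or higher thrombocytopenia is an adverse event of special interest. This covers the more serious changes, but depends on the investigator's judgment of significance and does not repair the graded table.
- **Shift summaries.** SAP 5.4 suggests that they are intended. However, no section defines one for laboratory data, so what will be produced is left open.

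A worst-grade count is also a legitimate descriptive summary, which argues for keeping it beside a baseline-referenced one. The denominator difference is minor: all-treated is not a population in protocol Table 20, but it reads naturally as the safety population.

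**Conclusion.** The point holds for the all-grades column. Followed as written, the plan reports laboratory abnormalities that were present at entry and only persisted as on-treatment toxicities, in a trial with no comparator. The Grade 3 or higher column is affected mainly for tests without an entry limit, and a reader should not infer that it is generally contaminated.

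The size cannot be estimated from the documents, because they do not say how many participants are abnormal at entry and never change grade. The figure of 4 to 16 of 40 rests wholly on the assumed 10% to 40% and on the abnormality appearing in at least one on-treatment test. Sample size, DLT evaluation and dose selection are untouched. This is an inexpensive improvement to safety reporting, not a flaw in the design.

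**What to change.** In SAP 4.7.2, with matching words in protocol 9.4.3.2:

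1. Make the laboratory toxicity summary the number and percentage of participants whose worst on-treatment grade exceeds their baseline grade, for all grades and for Grade 3 or higher.
2. Add a table of baseline grade by worst on-treatment grade for each Part and dose level or cohort. Give missing baselines their own row. They should not be treated silently as Grade 0, because any abnormality in those participants would then look new.
3. Keep the existing worst-grade count beside these if wanted, labelled as not adjusted for baseline.
4. Use one denominator in both documents: safety-population participants with at least one on-treatment value for the test.
5. Settle whether laboratory abnormalities are primary or secondary in Part-1 and Part-3A, and make the synopsis, protocol 9.4.3 and SAP 4.3 agree.

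The cost is a wording change and one standard table from data already collected. The any-grade percentages in the main summary can only stay the same or become lower.

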9.4.4 Other endpoint(s)

Concentrations of SAR442720, pembrolizumab, and adagrasib will be summarized with descriptive statistics.

For Part-3A and Part-4, PK parameter estimates, including but not limiting to the ones listed below, will be determined when possible for SAR442720 and adagrasib:

- C_{max} (observed)
- T_{max} (observed)
- AUC_{0-t} and AUC_{inf} , if possible
- $t_{1/2}$, if possible
- Accumulation ratio

Unless otherwise specified, the PK parameters will be estimated based on noncompartmental analysis methods. These estimates will be summarized descriptively by dose cohort. All PK parameters will be computed using the actual elapsed time calculated relative to dose administration.

For Part-4, the geometric mean ratios and 90% confidence intervals of AUC and C_{max} will be computed for SAR442720 between fed and fasted states of tablet formulation (C1D1 to C1D15) and between the tablet (test) and capsule (reference) formulations (C1D15 to C2D1). In addition, the PK parameters in Part-4 will be analyzed using a mixed effect model, which will be described in detail in the statistical analysis plan.

Population PK analysis may be conducted to obtain the PK parameters of SAR442720, pembrolizumab, and adagrasib. If performed, the results will be summarized in a separate report.

Exploratory analyses may be performed to evaluate the relationship between the estimated PK parameters and PDs, selected safety, biomarker, or clinical effect endpoints.

The PK and PDy analyses will be presented in a separate report.

All other safety endpoints (ie, vital signs, ECG, ECOG, etc) will be summarized.

9.5 INTERIM ANALYSES

There is no formal interim analysis planned.

10 SUPPORTING DOCUMENTATION AND OPERATIONAL CONSIDERATIONS

10.1 APPENDIX 1: REGULATORY, ETHICAL, AND STUDY OVERSIGHT CONSIDERATIONS

10.1.1 Regulatory and ethical considerations

- This study will be conducted in accordance with the protocol and with the following:
 - Consensus ethical principles derived from international guidelines including the Declaration of Helsinki and the applicable amendments and Council for International Organizations of Medical Sciences (CIOMS) International Ethical Guidelines
 - Applicable ICH-GCP Guidelines
 - Applicable laws and regulations (eg, data protection law as General Data Protection Regulation - GDPR)
- The protocol, protocol amendments, ICF, IB, and other relevant documents (eg, advertisements) must be submitted to an IRB/IEC by the Investigator and reviewed and approved by the IRB/IEC before the study is initiated.
- Any amendments to the protocol will require IRB/IEC approval before implementation of changes made to the study design, except for changes necessary to eliminate an immediate hazard to study participants.
- The Investigator will be responsible for the following:
 - Providing written summaries of the status of the study to the IRB/IEC annually or more frequently in accordance with the requirements, policies, and procedures established by the IRB/IEC determining whether an incidental finding should be returned to a participant and, if it meets the appropriate criteria, to ensure the finding is returned (an incidental finding is a previously undiagnosed medical condition that is discovered unintentionally and is unrelated to the aims of the study for which the tests are being performed). The following should be considered when determining the return of an incidental finding:
 - The return of such information to the study participant (and/or his/her designated healthcare professional, if so designated by the participant) is consistent with all applicable national, state, or regional laws and regulations in the country where the study is being conducted, and
 - The finding reveals a substantial risk of a serious health condition or has reproductive importance, AND has analytical validity, AND has clinical validity.
 - The participant in a clinical study has the right to opt out of being notified by the Investigator of such incidental findings. In the event that the participant has opted out of being notified and the finding has consequences for other individuals, eg, the finding relates to a communicable disease, Investigators should seek independent ethical advice before determining next steps.

- In case the participant has decided to opt out, the Investigator must record in the site medical files that she/he does not want to know about such findings.
- Notifying the IRB/IEC of SAEs or other significant safety findings as required by IRB/IEC procedures.
- Providing oversight of the conduct of the study at the site and adherence to requirements of 21 Code of Federal Regulations (CFR), ICH guidelines, the IRB/IEC, European regulation 536/2014 for clinical studies (if applicable), and all other applicable local regulations.

As applicable, according to Directive 2001/20/EC, the Sponsor will be responsible for obtaining approval from the Competent Authorities of the EU Member States and/or Ethics Committees, as appropriate, for any amendments to the clinical trial that are deemed as “substantial” (ie, changes which are likely to have a significant impact on the safety or physical or mental integrity of the clinical trial participants or on the scientific value of the trial) prior to their implementation.

